8.2 Mean (+/- SEM) Serum AGT

Target population	:	PD Analysis Set
Analysis Items	:	Serum AGT
Group	:	Placebo, Zilebesiran 300 mg, Zilebesiran 600 mg, Total zilebesiran, Overall Total
Time of analysis	:	Refer to section 2.8.1
Content of analysis	:	
 • Trend diagram of Mean \pm SEM of measurement value and percent change from baseline will be presented graphically by groups, analysis visit in 6-Month DB period • Trend diagram of Mean \pm SEM of measurement value and percent change from baseline will be presented graphically by groups, analysis visit in 6-Month DB period and Safety/PD Follow-up period

8.3 Spaghetti Plot of Serum AGT

Target population	:	PD Analysis Set
Analysis Items	:	Serum AGT
Group	:	Placebo, Zilebesiran 300 mg, Zilebesiran 600 mg
Time of analysis	:	Refer to section 2.8.1
Content of analysis	:	
 • Spaghetti Plot for measurement value and percent change from baseline of AGT by group, analysis visit in 6-Month DB period • Spaghetti Plot for measurement value and percent change from baseline of AGT by group, analysis visit in 6-Month DB period and Safety/PD Follow-up period

8.4 Spaghetti Plot of Serum AGT by ADA Status during 6-Month DB Period

Target population	:	PD Analysis Set
Analysis Items	:	Serum AGT
Group	:	Placebo, Zilebesiran 300 mg, Zilebesiran 600 mg
Time of analysis	:	Refer to section 2.8.1
Content of analysis	:	
 • Spaghetti Plot for measurement value and percent change from baseline of AGT by group, patient and analysis visit in 6-Month DB period, ADA Status

9. Biomarker Evaluation

9.1 Summary of change from baseline in plasma renin concentration, plasma renin activity, and aldosterone

Target population	:	PD Analysis Set
-------------------	---	-----------------

Analysis Items	:	Plasma renin concentration, plasma renin activity, and aldosterone (Refer to Appendix 2)
Group	:	Placebo, Zilebesiran 300 mg, Zilebesiran 600 mg, Total zilebesiran, Overall Total
Time of analysis	:	Refer to section 2.8.1
Content of analysis	:	
 Calculate the summary statistics of change from baseline for plasma renin concentration, plasma renin activity, and aldosterone by groups and analysis time points.

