3. INVESTIGATIONAL PLAN

3.1. Summary of Study Design

This is a single dose, randomized, double-blind, placebo-controlled, parallel-group, Phase 1/2 study to evaluate the safety, tolerability, efficacy, PD, and PK of zilebesiran administered SC in Japanese patients with mild to moderate hypertension. A schematic of the study design is provided in [Figure 1](#).

Before randomization, patients will discontinue prior antihypertensive medication(s) (if taking) for a Washout period of a minimum of 3 weeks. Patients who meet all inclusion criteria and none of the exclusion criteria will be randomized 1:1:1, as described in [Section 3.4](#), to receive a single dose of 300 or 600 mg zilebesiran or placebo.

The planned enrollment for this study is 36 Japanese patients with mild to moderate hypertension. Each treatment arm will include 12 patients.

Eligible patients will be admitted to the site on Day -1, and patients who receive a dose of study drug on Day 1 will remain inpatient at the study site until discharge on Day 2. Patients will return to the clinical study site on an outpatient basis during the 6-month DB Treatment Period for safety, tolerability, efficacy, PD, and PK assessments, as outlined in the Schedule of Assessments ([Table 1](#)).

At Month 3, conventional oral antihypertensives may be added per Investigator judgement for 24-hour mean SBP ≥ 130 mmHg by ABPM. After Month 3, oral antihypertensive medications may also be added per Investigator judgement for persistent elevations in blood pressure (eg, office SBP ≥ 140 mmHg, home blood pressure monitoring [HBPM] SBP > 135 mmHg). [Williams 2018]

All patients will complete Safety/PD Follow-up visits and complete assessments as described in [Table 1](#) at Months 9 and 12.

The estimated duration of study participation, inclusive of screening and safety/PD follow-up, is 14 months.

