Months 3 to 6	
Treat to target blood pressure using a CCB and/or thiazide/thiazide-like diuretic:
 
 At Month 3, a CCB and/or a thiazide/thiazide-like diuretic may be added if the 24-hour mean SBP is ≥ 130 mmHg by ABPM. After Month 3, oral antihypertensive medications may also be added per Investigator judgement for persistent elevations in blood pressure (eg, systolic office blood pressure ≥ 140 mmHg or systolic HBPM >135 mmHg).[Williams 2018]
Safety Follow-up period	Treat to target blood pressure using Investigator's choice of oral antihypertensive(s).

Abbreviations: ABPM=ambulatory blood pressure monitoring; ACE=angiotensin converting enzyme; ARB=angiotensin II-receptor blocker; CCB=calcium channel blocker; DBP=diastolic blood pressure; eCRF=electronic case report form; HBPM=home blood pressure monitoring; RAS=renin-angiotensin system; SBP=systolic blood pressure.

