2.6 Efficacy Assessment

2.6.1 SBP and DBP

Analysis using censoring and analysis using all collected data will be conducted for ABPM and Office Blood Pressure. Analysis using all collected data will be conducted for HBPM

- Censoring data: ABPM/Office Blood Pressure that assessed while patients are on and within 2 weeks after stopping any escape anti-hypertensive medication will be excluded for analysis.
- All collected data: all collected BP data is included in analysis, regardless of the anti-hypertensive escape medication.

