2.8 Analysis Visit

2.8.1 Analysis item except PK data, 24-hour Holter ECG Extraction

Assessment	Analysis item	Analysis visit
Efficacy	24-hour ABPM (SBP and DBP)	Baseline, Month 3, Month 6
	OBP (SBP and DBP)	Baseline, Day 2, Day 3, Day 8, Day 15, Month 1, Month 2, Month 3, Month 4, Month 5, Month 6, Month 9 and Month 12
	HBPM (SBP and DBP)	Baseline, Week X (at least once per week after Day 2)
Pharmacodynamic (PD)	Serum AGT	Baseline, Day 8, Day 15, Month 1, Month 2, Month 3, Month 6, Month 9 and Month 12
Biomarker	RAS (Renin concentration, Renin activity assessment and Aldosterone assessment)	Baseline, Month 1, Month 2, Month 3 and Month 6
Safety	Vital sign	Baseline, Day 2, Day 3, Day 8, Day 15, Month 1, Month 2, Month 3, Month 4, Month 5, Month 6, Month 9 and Month 12
	Weight, Height and BMI	Baseline and Month 6
	Single 12-lead ECG	Baseline and Month 6
	Hematology	Baseline and Month 6
	Serum Chemistry	Baseline, Day 8, Day 15, Month 1, Month 2, Month 3, Month 4, Month 5, Month 6, Month 9 and Month 12
	Liver Function Tests	Baseline, Day 8, Day 15, Month 1, Month 2, Month 3, Month 4, Month 5, Month 6, Month 9 and Month 12
	Urinalysis	Baseline and Month 6
	Coagulation	Baseline and Month 6
	Glycemic Assessment	Baseline
	Pregnancy Testing/FSH	Baseline
Optional research samples (urine, plasma, serum)	-	Baseline, Month 3 and Month 6
ADA	ADA and titer results	Baseline, Month 1, Month 3, Month 6

Abbreviations: ABPM=ambulatory blood pressure monitoring; ADA=anti-drug antibody;

AE=adverse event; AGT=angiotensinogen; DBP=diastolic blood pressure;

ECG=electrocardiogram; PD=pharmacodynamics; PK=pharmacokinetics; RAS = renin-angiotensin system; SBP=systolic blood pressure; DNA=deoxyribonucleic acid; FSH=follicle stimulating hormone;

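### Month 6 renin, renin activity and aldosterone are summarised with no handling of escape antihypertensives, although the SAP censors ambulatory and office blood pressure for the same drugs

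*SAP*

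**What the plan says.** SAP 9.1 gives the RAS biomarker analysis in one line: "Calculate the summary statistics of change from baseline for plasma renin concentration, plasma renin activity, and aldosterone by groups and analysis time points". SAP 9.2 and 9.3 add mean and individual plots. The visits in SAP 2.8.1 are "Baseline, Month 1, Month 2, Month 3 and Month 6". The population is the PD Analysis Set, which requires only one full dose (SAP 2.2). None of these sections mentions added antihypertensives.

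Baseline is the last non-missing pre-dose value (SAP 4.1.2). Protocol 3.1 places it after washout: "Before randomization, patients will discontinue prior antihypertensive medication(s) (if taking) for a Washout period of a minimum of 3 weeks".

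Protocol Table 3 (section 5.7.2) changes the medication setting from Month 3: "At Month 3, a CCB and/or a thiazide/thiazide-like diuretic may be added if the 24-hour mean SBP is" at or above 130 mmHg. After Month 3, drugs may also be added for persistent elevation on office or home readings. Conventional RAS inhibitors are prohibited throughout (protocol 5.8.2).

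For blood pressure the SAP recognises the issue. Section 2.6.1 states: "Analysis using censoring and analysis using all collected data will be conducted for ABPM and Office Blood Pressure". The censored version follows this rule: "ABPM/Office Blood Pressure that assessed while patients are on and within 2 weeks after stopping any escape anti-hypertensive medication will be excluded for analysis". Home blood pressure is analysed as all collected data only.

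**The concern.** The stated objective is the effect of zilebesiran on RAS biomarkers. For a patient who starts a CCB or thiazide after Month 3, the Month 6 change compares a value on an added antihypertensive with a value off antihypertensives. For a patient who does not, both values are off antihypertensives. SAP 9.1 averages the two kinds of change.

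Escape depends on blood pressure, which the study drug is expected to lower. The mix is therefore likely to differ between placebo and zilebesiran. A reader comparing arms at Month 6, or Month 3 with Month 6 within an arm, could take an add-on drug effect for a study drug effect, or the reverse.

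**Working it through.** The plan states no figure on this point, so there is none to reproduce. The check has three parts.

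**1. Which RAS visits are exposed**

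| RAS visit | Add-on antihypertensives under protocol Table 3 |
|---|---|
| Baseline | None, after at least 3 weeks of washout |
| Months 1, 2 and 3 | Severe hypertension treated at any time; other escape only in restricted cases after Week 6 |
| Month 6 | Treat to target open since Month 3 |

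Month 3 is largely, but not wholly, free of add-on drugs. Month 6 is the only RAS visit after general add-on use opens.

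**2. Whether the arms should differ**

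Inputs from the protocol:
- Entry requires 24-hour SBP at or above 130 mmHg (section 4.1), the same value as the Month 3 add-on threshold.
- Study 002 showed placebo-corrected reductions at Month 3 of 16.7 mmHg (300 mg) and 15.7 mmHg (600 mg) (section 3.3).
- There are 12 patients per arm, so 12 on placebo and 24 on zilebesiran.

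Assumed, because the documents do not give them:
- baseline mean 138, 142 or 146 mmHg and SD 8 or 12, before truncation at 130;
- SD of change 8, 10 or 14 mmHg;
- placebo change -5, 0 or +5 mmHg.

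Model: Month 3 SBP = baseline + placebo change - effect + normal error. A patient is eligible for add-on if the result is at or above 130. The grid has 3 x 2 x 3 x 3 x 2 = 108 combinations, the last factor being the two effects. Simulated results:

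| Quantity | Minimum | Median | Maximum |
|---|---|---|---|
| Placebo eligible | 63% (7.6 of 12) | 85% | 98% (11.7 of 12) |
| Zilebesiran eligible | 13% (1.6 of 12 per arm) | 44% | 70% (8.5 of 12 per arm) |
| Placebo rate / zilebesiran rate, same scenario | 1.4 | | 5.2 |
| Placebo share of all eligible patients (12 vs 24) | 41% | 49% | 72% |

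The rate is higher in placebo in every scenario. The count need not be.

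**3. What this does to the Month 6 change**

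Let p be the share of an arm on an add-on drug at Month 6, and d the mean effect of that drug on the biomarker in its users, taken as equal across arms. The arm's mean change shifts by p x d, and the zilebesiran-minus-placebo difference shifts by (p_zilebesiran - p_placebo) x d.

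- 10% vs 25%: (0.10 - 0.25) x d = -0.15d
- 20% vs 50%: (0.20 - 0.50) x d = -0.30d
- 30% vs 75%: (0.30 - 0.75) x d = -0.45d
- 50% vs 50%: 0

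The documents give neither p nor d, and d may differ for each of the three markers.

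**The case against.** The endpoint is exploratory and the protocol plans only descriptive statistics with no formal testing. SAP 9.1 gives within-group summaries and no between-arm contrast. Protocol 7.2.5 asks for available PD data in all patients of the PD Analysis Set, so an all-collected summary follows the protocol. Add-on use is discretionary, and it may be a CCB alone. Other planned outputs help: escape proportion by visit (SAP 7.1.10), concomitant antihypertensives by group (12.5.1), individual biomarker plots (9.3), and listings 13.9 and 13.18.

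All of this stands and sets the priority. It does not close the gap: no planned summary separates biomarker values on add-on drugs from those off them, so the reader would have to join listings by hand.

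Four stronger readings are tempting but not supported:

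- **That the mixing falls mostly in placebo.** Only a higher rate is supported. With twice as many zilebesiran patients, placebo holds 41-72% of those eligible.
- **That it shrinks or hides the zilebesiran effect.** The documents do not say how a thiazide or CCB changes renin or aldosterone. Protocol 1.2 says zilebesiran is meant to reduce the downstream effects of angiotensin II. If aldosterone fell on zilebesiran and an add-on drug raised it in placebo, the gap would widen. If both treatments raised renin concentration, the gap would narrow.
- **That a size can be given.** Any percentage shift in placebo renin would be the product of an assumed number of diuretic users and an assumed fold change.
- **That baseline is drug-free.** It is free of antihypertensives only; protocol 5.8 allows stable SGLT2 inhibitors and certain alpha-blockers.

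**Conclusion.** The gap is confirmed from the text. The SAP handles escape drugs for ambulatory and office blood pressure but not for RAS biomarkers sampled at the same Month 6 visit, and baseline follows washout. A higher rate of escape eligibility in placebo than in each zilebesiran arm is expected from the shared 130 mmHg threshold and the Study 002 effect. That expectation assumes a similar effect in this population and the SBP distributions listed above. It concerns eligibility; actual use depends on investigator judgement. The Month 6 change can therefore mix study drug and add-on drug unequally across arms, by an unknown amount and in a direction that may differ by marker. No primary or secondary result is affected. This is a low-priority improvement.

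**What to change.** In SAP 9.1 and 9.2, keep the all-collected Month 6 summary and mean plot. Beside them, add a version that excludes samples taken while on, or within 2 weeks after stopping, an escape antihypertensive. This is the 2.6.1 rule. The visit flag in 2.8.3 can be reused because office blood pressure and RAS samples share the Month 6 visit. Show for each arm the number excluded and the number on a diuretic (ATC C03, already listed in SAP 2.5.3). Make the change before unblinding for the primary analysis.

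The cost is a short SAP edit, one repeated table and one repeated figure; no new data are collected. The downside is a smaller, selected group. If half of the eligible patients received an add-on drug (an assumption), exclusions would be 0.5 x 7.6 = 3.8 to 0.5 x 11.7 = 5.9 of 12 on placebo, and 0.5 x 1.6 = 0.8 to 0.5 x 8.5 = 4.2 of 12 per zilebesiran arm. Those remaining, especially on placebo, would be patients with lower blood pressure. The rule also removes patients on a CCB alone. For these reasons neither version should stand by itself.

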9.2 Mean (+/- SEM) Exploratory Biomarkers by Visit

Target population	:	PD Analysis Set
Analysis Items	:	Plasma renin concentration, plasma renin activity, and aldosterone (Refer to Appendix 2)
Group	:	Placebo, Zilebesiran 300 mg, Zilebesiran 600 mg
Time of analysis	:	Refer to section 2.8.1
Content of analysis	:	
 Trend diagram of Mean \pm SEM of measurement value and percent change from baseline will be presented graphically by groups, analysis visit in 6-Month DB period

9.3 Spaghetti Plot of Exploratory Biomarkers

Target population	:	PD Analysis Set
Analysis Items	:	Plasma renin concentration, plasma renin activity, and aldosterone (Refer to Appendix 2)
Group	:	Placebo, Zilebesiran 300 mg, Zilebesiran 600 mg
Time of analysis	:	Refer to section 2.8.1
Content of analysis	:	
 Spaghetti Plot for measurement value and percent change from baseline of each analysis item by group, analysis visit in 6-Month DB period

10. Anti-drug antibodies ADA

10.1 Summary of ADA Results

Target population	:	Safety Analysis Set
Analysis Items	:	Anti-drug antibodies (ADA)
Group	:	Placebo, Zilebesiran 300 mg, Zilebesiran 600 mg, Total zilebesiran, Overall Total
Time of analysis	:	Baseline, post-dose, treatment-emergent ADA
Content of analysis	:	
 Calculate the number of patients with the measurement value, ADA-positive at baseline by groups. and timepoint (baseline, post-dose and treatment-emergent ADA) Calculate the titer (min, max) by groups. and timepoint (baseline, post-dose and treatment-emergent ADA)

Definitions	:	• The denominator of proportions is the target population by groups.
-------------	---	--

11. Pharmacokinetics Evaluation

11.1 Summary of Plasma Zilebesiran Concentrations/ Urine Zilebesiran Concentrations/ Metabolite Plasma AS(N-1)3' Zilebesiran Concentrations/ Metabolite Urine AS(N-1)3' Zilebesiran Concentrations

Target population	:	PK Analysis Set
Analysis Items	:	Plasma zilebesiran concentrations, Urine zilebesiran concentrations, Metabolite plasma AS(N-1)3' zilebesiran concentrations, Metabolite urine AS(N-1)3' zilebesiran concentrations
Group	:	Zilebesiran 300 mg, Zilebesiran 600 mg
Time of analysis	:	Refer to section 2.8.2
Content of analysis	:	• Calculate the summary statistics of analysis items by groups and analysis time points.

11.2 Mean (+/- SEM) Plasma Zilebesiran Concentrations/ Urine Zilebesiran Concentrations/ Metabolite Plasma AS(N-1)3' Zilebesiran Concentrations/Metabolite Urine AS(N-1)3' Zilebesiran Concentrations - Linear Scale/Semi-logarithmic Scale

Target population	:	PK Analysis Set
Analysis Items	:	Plasma zilebesiran concentrations, Urine zilebesiran concentrations, Metabolite plasma AS(N-1)3' zilebesiran concentrations, Metabolite urine AS(N-1)3' zilebesiran concentrations
Group	:	Zilebesiran 300 mg, Zilebesiran 600 mg
Time of analysis	:	Refer to section 2.8.2
Content of analysis	:	• Trend diagram of Mean \pm SEM of measurement value will be presented graphically on both Linear Scale and Semi-logarithmic Scale by groups, analysis visit in 6-Month DB period

11.3 Spaghetti Plot of Plasma Zilebesiran Concentrations/Metabolite Plasma AS(N-1)3' Zilebesiran Concentrations by ADA Status - Linear Scale and Semi-logarithmic Scale

Target population	:	PK Analysis Set
Analysis Items	:	Plasma Zilebesiran concentrations, Metabolite plasma AS(N-1)3' zilebesiran concentrations
Group	:	Zilebesiran 300 mg, Zilebesiran 600 mg
Time of analysis	:	Refer to section 2.8.2
Content of analysis	:	• Spaghetti Plot for measurement value of each analysis items on both Linear Scale and Semi-logarithmic Scale by group, analysis visit in 6-Month DB period

11.4 Summary of Plasma Zilebesiran Pharmacokinetic Parameters/Metabolite Plasma AS(N-1)3' Zilebesiran Parameters

Target population	:	PK Analysis Set
Analysis Items	:	AUC ₀₋₂₄ , AUC _{0-last} , AUC _{0-t} , AUC _{0-inf} , AUC _{%extrap} , C _{max} , T _{max} , T _{1/2} , CL/F, Vz/F, λ_z for Zilebesiran. AUC ₀₋₂₄ , AUC _{0-last} , AUC _{0-t} , AUC _{0-inf} , AUC _{%extrap} , C _{max} , T _{max} , T _{1/2} , CL/F, Vz/F, λ_z , MRCMAX, MRAUC for AS(N-1)3' Zilebesiran.
Group	:	Zilebesiran 300 mg, Zilebesiran 600 mg
Content of analysis	:	
 Calculate the summary statistics of analysis items by groups. PK parameters: T_{1/2}, AUC_{0-inf}, CL/F, and Vz/F will be presented for only those patients in whom λ_z can be estimated.

11.5 Summary of Pooled urine Zilebesiran Pharmacokinetic Parameters/Metabolite Urine AS(N-1)3' Zilebesiran Parameters

Target population	:	PK Analysis Set
Analysis Items	:	Ae, fe, and CL _R
Group	:	Zilebesiran 300 mg, Zilebesiran 600 mg
Content of analysis	:	
 Calculate the summary statistics of analysis items by groups.

12. Safety Evaluation

12.1 Adverse Events

12.1.1 Overall summary of Treatment-emergent Adverse Events

Target population	:	Safety Analysis Set
Analysis Items	:	
 Treatment-emergent Adverse Events Study Drug Related Treatment-emergent Adverse Event Treatment-emergent Serious Adverse Events Study Drug Related Treatment-emergent Serious Adverse Events Severe Treatment-emergent Adverse Events Study Drug Related Severe Treatment-emergent Adverse Events Treatment-emergent Adverse Events leading to withdrawal from study Study Drug Related Treatment-emergent Adverse Events leading to withdrawal from study Death
Group	:	Placebo, Zilebesiran 300 mg, Zilebesiran 600 mg, Total zilebesiran, Overall Total
Content of analysis	:	
 Calculate the number of patients with the event and the percentages, the number of events by groups.
Definitions	:	
 The denominator of proportions is the target population by groups.

		
 • For Death, all fatal serious AEs are summarized, regardless of treatment-emergent classification.
--	--	---

12.1.2 Summary of Treatment-emergent Adverse Events by SOC and PT

Target population	:	Safety Analysis Set
Analysis Items	:	
 • Treatment-emergent Adverse Events • Study Drug Related Treatment-emergent Adverse Events • Treatment-emergent Serious Adverse Events • Study Drug Related Treatment-emergent Serious Adverse Events • Treatment-emergent Adverse Events leading to withdrawal from study • Treatment-emergent Adverse Events leading to death • Hepatic Treatment-emergent Adverse Events including AEs of LFT abnormalities • Treatment-emergent Adverse Events of Hyperkalemia • Treatment-emergent Adverse Events of Hypotension and Potential Hypotension • Treatment-emergent Adverse Events of Acute Renal Failure
Group	:	Placebo, Zilebesiran 300 mg, Zilebesiran 600 mg, Total zilebesiran, Overall Total
Content of analysis	:	
 • The number of patients with the event and the percentage, the number of events will be calculated for each group.
Definitions	:	
 • The denominator of proportions is the target population by groups. • Hepatic AEs, including AEs of Liver Function Test (LFT) abnormalities (SMQ all narrow and broad terms) • Hyperkalemia (CMQ) (Refer to Appendix 3) • Hypotension (FMQ narrow terms) • Potential Hypotension (Refer to Appendix 3) • Acute renal failure (SMQ all narrow and broad terms)

12.1.3 Summary of Treatment-emergent Adverse Events by Maximum Severity by SOC and PT

Target population	:	Safety Analysis Set
Analysis Items	:	Treatment-emergent Adverse Events, Study Drug Related Treatment-emergent Adverse Events
Group	:	Placebo, Zilebesiran 300 mg, Zilebesiran 600 mg, Total zilebesiran, Overall Total
Content of analysis	:	
 • The number of patients with the event, and the percentage will be calculated by groups and severity. • For symptoms (SOC, PT), the number of patients with symptoms and the percentage will be calculated by groups and severity.
Definitions	:	
 • Severity: Mild, Moderate, Severe • If multiple AEs with the same SOC (PT for the PT tabulation) occurs to the same patient, then count that patient into the worst severity. • The denominator of proportions is the target population by groups.

12.1.4 Summary of Treatment-emergent Adverse Events by PT

Target population	:	Safety Analysis Set
Analysis Items	:	Treatment-emergent Adverse Events, Study Drug Related Treatment-emergent Adverse Events, Treatment-emergent Serious Adverse Events
Group	:	Placebo, Zilebesiran 300 mg, Zilebesiran 600 mg, Total zilebesiran, Overall Total
Content of analysis	:	
 The number of patients with the event and the percentage, the number of events will be calculated for each group.
Definition	:	
 The denominator of proportions is the target population by groups.

